**Table 6-8 Creatinine alterations suspected to be related to spartalizumab or spartalizumab/LAG525**

Grade (CTCAE v5)	Mandatory Dose Modification
Grade 2 (> 1.5 - 3.0 x ULN, or >1.5-3.0 x baseline if baseline was elevated)	
Interrupt spartalizumab/LAG525 until recovery to ≤ grade 1 or baseline
 
 
Restart spartalizumab/LAG525 at the same dose level
 

Grade 3 (> 3.0 - 6.0 x ULN; or >3x baseline if baseline was elevated)	Permanently discontinue spartalizumab/LAG525
Grade 4 (> 6.0 x ULN)	Permanently discontinue spartalizumab/LAG525

**Table 6-9 Pneumonitis suspected to be related to spartalizumab or spartalizumab/LAG525**

Grade (CTCAE v5)	Mandatory dose modification
Grade 2	1st occurrence Interrupt spartalizumab/LAG525 until recovery to grade ≤ 1 or baseline 
 
Restart spartalizumab/LAG525 at the same dose level
 
 2nd occurrence Permanently discontinue spartalizumab/LAG525
Grade 3 or 4	Permanently discontinue spartalizumab/LAG525

**Table 6-10 Endocrinopathies suspected to be related to spartalizumab or spartalizumab/LAG525**

Grade (CTCAE v5)	Mandatory dose modification
Symptomatic endocrinopathies (e.g. hypophysitis, adrenal insufficiency, hypothyroidism, hyperthyroidism)	Interrupt spartalizumab/LAG525 until recovery to mild or no symptoms, and controlled with hormone replacement therapy 
 
Once recovered or controlled with hormone replacement, restart spartalizumab/LAG525 at the same dose level
 
 Hypothyroidism may be managed with replacement therapy without study treatment interruption (unless life-threatening) Permanently discontinue spartalizumab/LAG525 for any life-threatening endocrinopathies (i.e. hyperthyroidism, adrenal insufficiency, hypophysitis) or recurring severe/life-threatening events which cannot be controlled with replacement therapy
Autoimmune diabetes (Grade 3 or symptomatic hyperglycemia)	1st occurrence Interrupt spartalizumab/LAG525 until recovery to grade 1 or baseline 
 
Restart spartalizumab/LAG525 at the same dose level
 
 2nd occurrence Permanently discontinue spartalizumab/LAG525
Autoimmune diabetes (Grade 4 hyperglycemia or life-threatening complications)	Permanently discontinue spartalizumab/LAG525

**Table 6-11 Infusion reactions and cytokine release syndrome suspected to be related to spartalizumab or spartalizumab/LAG525**

Grade (CTCAE v5)	Mandatory dose modification
Grade 2	Permanently discontinue spartalizumab/LAG525 in case of recurring infusion reaction despite adequate premedication and prolonged infusion/slow infusion rate
Grade 3 or 4	Permanently discontinue spartalizumab/LAG525

**Table 6-12 Other adverse events suspected to be related to spartalizumab or spartalizumab/LAG525**

Grade (CTCAE v5)	Mandatory dose modification
Grade 3	1st occurrence Interrupt spartalizumab/LAG525 until recovery to ≤ grade 1 or baseline 
 
Restart spartalizumab/LAG525 treatment at the same dose level
 
 2nd occurrence Permanently discontinue spartalizumab/LAG525
Grade 4	Permanently discontinue spartalizumab/LAG525
Encephalitis (any Grade) or aseptic meningitis Guillain-Barre Severe peripheral or autonomic neuropathy, or transverse myelitis	Permanently discontinue spartalizumab/LAG525
Myasthenia gravis	Grade 2 
 
Interrupt spartalizumab/LAG525 until recovery to ≤ Grade 1 or baseline
 

Grade (CTCAE v5)	Mandatory dose modification
	Grade ≥3 
 
Permanently discontinue spartalizumab/LAG525
 

Myocarditis (any grade) or other cardiac events Grade ≥ 3	Permanently discontinue spartalizumab/LAG525 (refer to Table 14-17 for recommended management guidelines for those events)
Pancreatitis Amylase/lipase elevation	Grade 2 acute pancreatitis 
 
Interrupt spartalizumab/LAG525 until recovery to ≤ Grade 1 or baseline
 
 Grade ≥3 acute pancreatitis: 
 
Permanently discontinue spartalizumab/LAG525
 

Autoimmune hemolytic anemia, hemolytic uremic syndrome, or acquired hemophilia grade ≥3	Permanently discontinue spartalizumab/LAG525
Ocular events	Grade 2 
 
Interrupt spartalizumab/LAG525 until recovery to ≤ Grade 1 or baseline
 
 Grade 3 and 4 
 
Permanently discontinue spartalizumab/LAG525
 

### 6.3.1.4 Mandatory dose modifications for capmatinib

All dose modifications should be based on the worst preceding toxicity. Capmatinib dose reduction must follow the dose reduction steps described in [Table 6-3](#) in [Section 6.3.1.1](#). Dose escalation after previous dose reduction due to an adverse event is allowed as described in [Section 6.2](#).

**Table 6-13 Hematological adverse events suspected to be related to capmatinib**

Grade (CTCAE v5)	Mandatory dose modifications
Neutrophil count decreased (ANC)	
Grade 3	Interrupt capmatinib until recovery to grade ≤ 2 
 
If resolved ≤ 7 days, restart at the same dose level
 
If not resolved within 7 days, restart at reduced dose level
 

Grade 4	Interrupt capmatinib until recovery to ≤ grade 2, then restart at reduced dose level
Febrile neutropenia	
	Interrupt capmatinib 
 
If resolved in ≤ 7 days, restart at reduced dose level
 
If not resolved within 7 days, permanently discontinue capmatinib
 

Thrombocytopenia	
Grade 3 without clinically significant bleeding	Continue capmatinib at the same dose level
Grade 3 with clinically significant bleeding	Interrupt capmatinib until recovery to grade ≤ 2 
 
If resolved ≤ 7 days, restart at the same dose level
 
If not resolved within 7 days, restart at reduced dose level
 

Grade 4	Interrupt capmatinib until recovery to grade ≤ 2, then restart at reduced dose level. If toxicity recurs, permanently discontinue capmatinib

**Table 6-14 Creatinine alterations suspected to be related to capmatinib**

Grade (CTCAE v5)	Mandatory dose modifications
Grade 2 (> 1.5 - 3.0 x ULN; or >1.5-3.0 x baseline if baseline was elevated) OR Grade 3 (> 3.0 - 6.0 x ULN; or >3x baseline if baseline was elevated )	Interrupt capmatinib until recovery to grade ≤ 1 or baseline 
 
If resolved in ≤ 7 days: restart capmatinib at reduced dose level
 
If not resolved within 7 days, permanently discontinue capmatinib
 

Grade 4 (> 6.0 x ULN)	Permanently discontinue capmatinib

**Table 6-15 Abnormal liver test results suspected to be related to capmatinib**

Grade (CTCAE v5)	Mandatory dose modifications
Isolated total bilirubin elevation - For patient's whose baseline total bilirubin is ≤ ULN	
Grade 1 (>ULN - 1.5 x ULN)	Maintain dose level of capmatinib and monitor liver enzymes
Grade 2 (>1.5 - 3.0 x ULN)	Interrupt capmatinib until recovery to grade ≤ 1 
 
• If resolved in ≤ 7 days, restart at the same dose level
 
• If not resolved within 7 days, restart at reduced dose level
 

Grade 3 (>3.0 - 10.0 x ULN) c	Interrupt capmatinib until recovery to grade ≤ 1, 
 
• If resolved in ≤ 7 days, restart at reduced dose level
 
• If not resolved within 7 days, permanently discontinue capmatinib
 

Grade 4 (>10.0 x ULN)	Permanently discontinue capmatinib
Isolated total bilirubin elevation - For patient's whose baseline total bilirubin is > ULN b	
Grade 1 > 1.0 - 1.5 x baseline if baseline was abnormal	Maintain dose level of capmatinib and monitor liver enzymes.
Grade 2 >1.5 – 3.0 × above baseline if baseline was abnormal	Interrupt capmatinib until recovery to baseline 
 
• If resolved in ≤ 7 days, restart at the same dose level
 
• If not resolved within 7 days, restart at reduced dose level
 

Grade 3 >3.0 -10x above baseline if baseline was abnormal	Interrupt capmatinib until recovery to baseline 
 
• If resolved in ≤ 7 days, resume treatment at reduced dose level
 
• If not resolved within 7 days, permanently discontinue capmatinib
 

Grade 4 (> 10.0 × ULN) b if baseline was abnormal	Permanently discontinue capmatinib
Isolated AST or ALT elevation for patient's baseline AST/ALT are ≤ ULN	
Grade 1 and 2 (> ULN - 5.0 × ULN)	Maintain dose level of capmatinib
Grade 3 (> 5.0 – 20.0 × ULN)	Interrupt capmatinib until recovery to grade ≤ 1, 
 
• If resolved in ≤ 7 days, restart treatment at reduced dose level
 
• If not resolved within 7 days, permanently discontinue capmatinib
 

Grade 4 (>20.0 × ULN)	Permanently discontinue capmatinib
Isolated AST or ALT elevation for patient's baseline AST or ALT are > ULN	
Grade 2 (> 3.0 – 5.0 × baseline value)	Interrupt capmatinib until recovery to grade ≤ 1 or baseline 
 
• If resolved in ≤ 7 days, restart at reduced dose level
 
• If not resolved within 7 days, permanently discontinue capmatinib
 

Grade ≥ 3 (> 5.0 × baseline value)	Permanently discontinue capmatinib
Combined a, d elevations of AST or ALT and total bilirubin	
For patients with normal baseline ALT or AST or total bilirubin value: AST or ALT >3.0 × ULN combined with total bilirubin >2.0 × ULN without evidence of cholestasis c OR For patients with elevated baseline AST or ALT or total bilirubin value [AST or ALT >2 × baseline AND > 3.0 × ULN] OR [AST or ALT > 8.0 × ULN], combined with [total bilirubin >2x baseline] AND >2.0 × ULN without evidence of cholestasis c	Permanently discontinue capmatinib in the absence of signs of cholestasis, hemolysis, and alternative causes of the liver injury have been excluded (e.g., concomitant use of hepatotoxic drug(s), alcoholic hepatitis, etc.).
a 'Combined' defined as: total bilirubin increase to the defined threshold concurrently with ALT/AST increase to the defined threshold.	

Grade (CTCAE v5)	Mandatory dose modifications
	
b If total bilirubin > 3.0 x ULN is due to the indirect (non-conjugated) component only, and hemolysis as the etiology has been ruled out as per institutional guidelines (e.g. review of peripheral blood smear and haptoglobin determination), then ↓ 1 dose level and continue treatment at the discretion of the Investigator.
 
c 'Cholestasis' defined as: ALP elevation (> 2 x ULN and R value (ALT/ALP in x ULN) < 2) in patients without bone metastases, or elevation of ALP liver fraction in patients with bone metastases. Note: The R value is calculated by dividing the ALT by the ALP, using multiples of the ULN for both values. It denotes whether the relative pattern of ALT and/or ALP elevation is due to cholestasis (R≤2), hepatocellular (R≥5), or mixed (R>2 and <5) liver injury.
 
d If combined elevations of AST or ALT and total bilirubin do not meet the defined thresholds, please follow the instructions for isolated elevation of AST/ALT, and take a conservative action based on the degree of the elevations (e.g., discontinue treatment at the situation when omit dose is needed for one parameter and discontinue treatment is required for another parameter). After all elevations resolve to the defined thresholds that allow treatment re-initiation, re-start treatment either at the same dose or one dose lower if meeting a criterion for dose reduction.

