**Hepatic**

- Total bilirubin  $\leq 1.5 \times$  ULN (upper limit of normal)
- AST  $\leq 3.0 \times$  ULN, except for subjects with liver metastasis, who may only be included if AST  $\leq 5.0 \times$  ULN
- ALT  $\leq 3.0 \times$  ULN, except for subjects with liver metastasis, who may only be included if ALT  $\leq 5.0 \times$  ULN

- 10a. Subjects must have recovered from treatment-related toxicities of prior anticancer therapies to grade  $\leq 1$  (CTCAE v 5.0).

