**Table 6-27 Hepatic adverse events suspected to be related to canakinumab**

Grade (CTCAE v5)	Mandatory dose modifications
Isolated total Bilirubin elevation	
Grade 2 (> 1.5 - 3.0 $\times$ ULN; >1.5 - 3.0 $\times$ baseline if baseline was abnormal)	Interrupt canakinumab and monitor liver test a weekly, or more frequently if clinically indicated, until resolved to $\leq$ 1.5 $\times$ ULN 
 
• If resolved in <math>\leq</math> 14 days, restart at same dose level
 

Grade (CTCAE v5)	Mandatory dose modifications
	
 
• If not resolved within 14 days, permanently discontinue canakinumab
 

Grade 3 (> 3.0 - 10.0 × ULN*; >3.0 - 10.0 x baseline if baseline was abnormal)	Interrupt canakinumab and monitor liver test a weekly, or more frequently if clinically indicated, until resolved to ≤ 1.5 × ULN 
 
• If resolved in ≤ 14 days, then restart at the same dose level
 
• If not resolved within 14 days, permanently discontinue canakinumab. The subject should be monitored weekly (including liver testa), or more frequently if clinically indicated, until total bilirubin have resolved to baseline or stabilization over 4 weeks.
 

Grade 4 (> 10.0 × ULN*; >10.0 x baseline if baseline was abnormal)	Permanently discontinue canakinumab. The subject should be monitored weekly (including liver test a ), or more frequently if clinically indicated, until total bilirubin have resolved to baseline or stabilization over 4 weeks.
Isolated AST or ALT elevation	
Grade 2 (> 3.0 - 5.0 × ULN; >3.0 - 5.0 x baseline if baseline was abnormal)	Continue canakinumab at the same dose level Repeat liver test a within 48-72 hours; if abnormal values are confirmed upon the repeat test, then monitor liver test a weekly, or more frequently if clinically indicated, until resolved to ≤ 3.0 × ULN
Grade 3 > 5.0 - 10.0 × ULN; >5.0 – 10 x baseline if baseline was abnormal	Interrupt canakinumab. Repeat liver test a within 48-72 hours; monitor liver test a weekly, or more frequently if clinically indicated, until resolved to ≤ 3.0 × ULN. 
 
• If resolved in ≤ 28 days, restart canakinumab at same dose
 
• If not resolved within 28 days, permanently discontinue canakinumab
 

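### Table 6-15 (capmatinib): with a raised baseline, bilirubin above 10 x ULN but not above 10 x baseline falls in both the grade 3 and the grade 4 row, which prescribe different actions

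*Protocol*

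**What the plan says.** Table 6-15 (Section 6.3.1.4) splits isolated bilirubin elevation into two blocks by baseline value; each heading begins "For patient's whose baseline total bilirubin is" and then gives the condition.

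- **Baseline at or below ULN.** All four grades are multiples of ULN and follow one another without overlap.
- **Baseline above ULN.** Grades 1 to 3 are multiples of baseline, with grade 3 given as "Grade 3 >3.0 -10x above baseline if baseline was abnormal". Grade 4 in the same block is given as "Grade 4 (> 10.0 × ULN" and is also labelled for an abnormal baseline.

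In the raised-baseline block, grade 3 calls for interruption until recovery to baseline, followed by one of two branches: "If resolved in ≤ 7 days, resume treatment at reduced dose level" or "If not resolved within 7 days, permanently discontinue capmatinib". Grade 4 calls for permanent discontinuation at once.

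Footnote b, attached to the raised-baseline heading and to its grade 4 row, covers bilirubin above 3.0 x ULN that is unconjugated only, with hemolysis excluded. The dose then drops one level and the site may "continue treatment at the discretion of the Investigator".

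Section 6.3.1 makes these tables mandatory and does not permit deviations from interruptions or reductions. Inclusion criterion 9a (Section 5.2.1) caps total bilirubin at 1.5 x ULN at screening.

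**The concern.** Adjacent grades in one block should divide the scale so that a value has one grade and one action. Here the measuring unit changes between grade 3 and grade 4. Since the block is defined by a baseline above ULN, 10 x baseline always lies above 10 x ULN, so the upper part of grade 3 is also grade 4 for every subject the block covers.

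At stake is consistent handling of a serious liver signal. Two sites could see the same value, each follow a row as written, and act differently: one interrupts and may later resume, the other stops the drug for good. Because the rules are mandatory, either action could also be recorded as a deviation from the other row.

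**Working it through.** The plan gives no figure to reproduce. The check is an interval comparison in units of ULN.

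**Inputs**

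- b = baseline bilirubin / ULN. The block requires b > 1; the entry criterion gives b ≤ 1.5, taking the baseline value to lie within the entry limit.
- Grade 3: above 3.0 and up to 10 times baseline, which is (3b, 10b] x ULN.
- Grade 4: above 10 x ULN, which is (10, ∞).

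**Overlap.** The intersection is (10, 10b], non-empty for every b > 1. Its share of the grade 3 band is (10b − 10) / (10b − 3b) = (10b − 10) / 7b.

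| b | Grade 3 (x ULN) | Overlap (x ULN) | Share of grade 3 band |
|---|---|---|---|
| 1.1 | 3.3 to 11 | 10 to 11 | 1/7.7 = 13% |
| 1.2 | 3.6 to 12 | 10 to 12 | 2/8.4 = 24% |
| 1.3 | 3.9 to 13 | 10 to 13 | 3/9.1 = 33% |
| 1.4 | 4.2 to 14 | 10 to 14 | 4/9.8 = 41% |
| 1.5 | 4.5 to 15 | 10 to 15 | 5/10.5 = 48% |

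The share is a share of the band's width, not of subjects or events. If the grade 3 wording is read literally as an increase over baseline, its upper end becomes 11b, or 16.5 x ULN at b = 1.5, and the overlap widens.

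**Example.** With baseline 1.4 x ULN and an on-treatment value of 12 x ULN, the ratio to baseline is 12 / 1.4 = 8.6. That is within grade 3, while 12 > 10 is grade 4.

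**Actions in the overlap**

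| | Grade 3 row | Grade 4 row | Conflict |
|---|---|---|---|
| At onset | Interrupt | Permanently discontinue | Yes |
| Back to baseline within 7 days | Resume at reduced dose | Permanently discontinue | Yes |
| Not back to baseline within 7 days | Permanently discontinue | Permanently discontinue | Only on timing |

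**Check on the cause.** With one common reference the bands are (3b, 10b] and above 10b, or (3, 10] and above 10. Neither pair overlaps, so the mixed reference is the whole cause.

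**The case against.** **The worst-toxicity rule.** Sections 6.3.1 and 6.3.1.4 base dose modifications on the worst toxicity so far, and it can be argued that the higher grade then governs. This is a sensible working reading. But the rule presupposes a grade for each value; it does not say which reference grades this one. Footnote d's call for conservative action concerns AST/ALT and bilirubin raised together, so it does not settle an isolated elevation either.

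**A ULN-based grade 4 may be deliberate.** Dose rules are drug-specific, and the creatinine tables (6-8, 6-14, 6-26) also give grade 3 a baseline alternative while fixing grade 4 to ULN. This stands against inferring that baseline is the right unit merely because Table 6-27 for canakinumab states its grade 4 as ">10.0 x baseline if baseline was abnormal". The comparison shows only that the protocol elsewhere writes the same grade without an overlap. A repeated convention does not assign a value to one row.

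**Stronger readings that the text does not support.**

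- A reader might infer that overlapping values require both restart and permanent discontinuation. They do not: grade 3 allows resumption only on recovery within 7 days and otherwise also ends in a permanent stop.
- A reader might count footnote b as a third conflicting action. It is a conditional exception to the rows it is attached to, not a contradiction of them.
- A reader might conclude that the unconjugated-bilirubin exception belongs on the normal-baseline grade 3 row, which carries footnote c (the cholestasis definition). That rests on one superscript in text extracted from a PDF, so it justifies a check of the source table and no more.

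**Practical reach.** Arm 2 was declared futile at interim analysis 1 and its enrollment stopped (Section 4.1.1), after 43 subjects had been treated (Amendment 5 rationale). If AST or ALT also passes the combined thresholds without cholestasis, a separate row of Table 6-15 applies. These points stand and limit the importance of the issue.

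**Conclusion.** The point holds in a narrow form. For capmatinib subjects with a raised baseline, isolated total bilirubin above 10 x ULN and up to 10 x baseline (at most 15 x ULN at the entry limit) meets two mandatory rows. They disagree on interruption versus discontinuation at onset, and on restart versus permanent stop when the value returns to baseline within 7 days. Final outcomes differ only in that second situation, which needs a fall from above 10 x ULN to no more than 1.5 x ULN in a week.

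This is an internal contradiction in current text, of minor consequence. It affects no endpoint, sample size or analysis. The conclusion assumes that baseline lies within the entry limit and that the value falls outside footnote b's exception. That such values are rare is a judgement, since the protocol reports no frequency. The document also does not say how many arm 2 subjects remain on capmatinib. It does not establish which of the two references is correct, and none is suggested here.

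**What to change.** Rewrite the raised-baseline grade 3 and grade 4 bilirubin rows of Table 6-15 so that every value falls in exactly one row. The clinical team chooses the reference. In the same edit, check against the source table that footnotes b and c sit on the rows they were meant for. If any arm 2 subject is still taking capmatinib, tell the sites which row applies in the meantime.

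The cost is an edit to one table, which can go into the next amendment. No data collection, analysis or sample size changes.

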**Table 6-16 Pancreatitis, amylase and lipase elevations suspected to be related to capmatinib**

Grade (CTCAE v5)	Mandatory dose modification
Pancreatitis	
Grade ≥ 3	Permanently discontinue capmatinib
Asymptomatic amylase and/or lipase elevation	
Grade 3 (> 2.0 - 5.0 × ULN with signs or symptoms; >5.0 x ULN and asymptomatic)	Interrupt capmatinib until resolved to grade ≤ 2 
 
• If resolved in ≤ 14 days, restart at same dose level
 
• If not resolved within 14 days, restart at reduced dose level
 

Grade 4 (> 5.0 × ULN and with signs or symptoms)	Permanently discontinue capmatinib
Symptomatic elevations	
Any grade	Permanently discontinue capmatinib

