## 6.3 Dose modifications

### 6.3.1 Mandatory dose modification and dose delay

For subjects who do not tolerate the protocol-specified dosing schedule, dose interruptions and/or reductions are mandated for treatment-related adverse events in order to manage subject safety and allow subjects to continue the study treatment.

Dose reductions are only allowed for capmatinib and ribociclib (refer to [Section 6.3.1.1](#)). Dose changes for spartalizumab, LAG525 and canakinumab are prohibited.

[Table 6-2](#) summarizes the mandatory dose modifications for specific treatment-related adverse events. If the specific adverse event is not listed, the guideline for ‘Other adverse events’ must be followed. AEs are to be graded according to NCI-CTCAE v5 ([ctep.cancer.gov](http://ctep.cancer.gov)) and all dose modifications should be based on the worst preceding toxicity. Deviations to mandatory dose interruptions and/or reductions are not allowed. Permanent treatment discontinuation is mandatory for specific events indicated as such in [Table 6-5](#) to [Table 6-37](#) and in [Section 6.3.1.5](#) or listed in [Section 7.1.5](#).

The investigator must follow the dose modifications for the study drug suspected to be related to the event:

- If the event is suspected to be related to spartalizumab, the investigator must follow the dose modifications specific for spartalizumab.
- If the event is suspected to be related to LAG525 or capmatinib or canakinumab or ribociclib, the investigator must follow the dose modifications specific for the suspected study drug.
- If it cannot be distinguished which of the study drugs within the combination is suspected to be related to the event, the investigator must follow the dose modifications specific to both study drugs within the combination.

Recommended management guidelines for suspected immune-related adverse events are provided in [Appendix 3](#) and can be amended according to the local or institutional guidelines.

Except for arm 1 where spartalizumab and LAG525 must be permanently discontinued at the same time, it is allowed for the other arms to discontinue one of the two study drugs within the combination. Permanent study treatment discontinuation is defined as the permanent discontinuation of both study drugs within the combination arm.

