### 6.3.1.2 Maximum duration of study drug(s) interruption

If the treatment with spartalizumab is interrupted for more than 12 weeks (counted from the time the AE reaches a grade that leads to spartalizumab interruption), spartalizumab must be permanently discontinued.

If the treatment with LAG525 is interrupted for more than 12 weeks (counted from the time the AE reaches a grade that leads to LAG525 interruption), LAG525 must be permanently discontinued.

If the treatment with capmatinib is interrupted for more than 3 consecutive weeks (counting from the first day when a dose was interrupted), then capmatinib must be permanently discontinued.

If the treatment with ribociclib is interrupted for more than 28 consecutive days due to ribociclib-related toxicity (counting from the first day when a dose was interrupted, including the 7 days of planned interruption of dosing between Day 22-28 of a cycle), then ribociclib must be permanently discontinued.

If the treatment with canakinumab is interrupted for more than 4 weeks (counted from the intended day of the next scheduled dose), canakinumab must be permanently discontinued.

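### Table 6-16 (capmatinib) orders both restart and permanent discontinuation for a symptomatic amylase or lipase rise of >2.0–5.0 × ULN

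*Protocol*

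**What the plan says.** Protocol Section 6.3.1.4, Table 6-16, has three blocks: pancreatitis, asymptomatic amylase and/or lipase elevation, and symptomatic elevations.

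- **Asymptomatic block, grade 3 row.** It is defined as "Grade 3 (> 2.0 - 5.0 × ULN with signs or symptoms; >5.0 x ULN and asymptomatic". Capmatinib is interrupted until the rise is grade 2 or lower. Then: "If resolved in ≤ 14 days, restart at same dose level" and "If not resolved within 14 days, restart at reduced dose level".
- **Asymptomatic block, grade 4 row.** It is defined as "Grade 4 (> 5.0 × ULN and with signs or symptoms" and orders permanent discontinuation.
- **Last block, "Symptomatic elevations".** There is one row, any grade, and it orders permanent discontinuation.

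Three rules elsewhere bear on this:

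- Section 6.3.1: "Deviations to mandatory dose interruptions and/or reductions are not allowed".
- Section 6.3.1: "Permanent treatment discontinuation is mandatory for specific events indicated as such in" Tables 6-5 to 6-37, among other places.
- Section 6.3.1.2 sets a limit: "If the treatment with capmatinib is interrupted for more than 3 consecutive weeks", the drug must be stopped for good.

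**The concern.** A capmatinib-related rise of >2.0–5.0 × ULN with signs or symptoms fits the grade 3 row by its bracketed definition and the last block by its title. The first tells the site to rechallenge and the second forbids it. Both sit in a column of mandatory actions.

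What is at stake is patient safety. A site that grades the event first and follows the grade 3 row as written gives capmatinib again to a patient who had a symptomatic pancreatic enzyme rise. Section 2.6.2 treats the pancreas as a recognised concern for this drug: it reports acinar cell changes in rats and monkeys, and enzyme elevations during clinical development.

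**Working it through.** No planned statistical figure is involved, so the main check sets each combination of level and symptoms against the rows of Table 6-16.

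| Event | Rows met | Action | Conflict |
|---|---|---|---|
| >5.0 × ULN, asymptomatic | Grade 3 | Interrupt, restart | None |
| >5.0 × ULN, symptomatic | Grade 4; symptomatic any grade | Discontinue; discontinue | None in action |
| >2.0–5.0 × ULN, symptomatic | Grade 3; symptomatic any grade | Interrupt, restart; discontinue | **Yes** |
| Lower level, symptomatic | Symptomatic any grade | Discontinue | None |

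Only the third line conflicts.

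**Is there a precedence rule?**

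- Table 6-16 has no footnote. The footnote advising the conservative action belongs to Table 6-15 and concerns liver tests.
- Section 6.3.1 says what to do when it is unclear which of the two drugs caused an event. It does not say what to do when two rows of one table match.
- The worst-preceding-toxicity rule in Section 6.3.1.4 does not help, because both rows describe the same event at the same severity.
- The heading of the asymptomatic block does not settle it either, since the grade 4 row beneath it is defined by symptoms.

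**How long can the rows differ?** Counting from the first interrupted dose:

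- Resolved by day 14: the grade 3 row restarts at the same dose; the last row discontinues.
- Resolved on days 15–21: the grade 3 row restarts at a reduced dose; the last row discontinues.
- Not resolved by day 21: Section 6.3.1.2 forces discontinuation, so both rows give the same result.

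**How many subjects?** The documents give no rate for the conflicting cell, so this is only a loose ceiling based on a broader event.

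- Inputs: 43 subjects treated in arm 2 (Amendment 5 rationale). Suspected grade 3/4 lipase rise in 9 patients (4.1%) and amylase rise in 1 patient (0.5%) in a single-agent study (Section 2.6.2).
- Lipase: 43 × 0.041 = 1.76, about 1.8 subjects. Amylase: 43 × 0.005 = 0.22, about 0.2.
- Range for lipase: 9 patients at 4.1% implies a denominator of 217 to 222. Taking 220, the exact 95% interval for 9/220 is 1.9% to 7.6%; times 43, this is 0.8 to 3.3 subjects.
- Only symptomatic rises of >2.0–5.0 × ULN enter the cell. In the nine-patient capmatinib–nivolumab cohort (Section 1.2.3.2.2), both grade 3 or higher lipase rises were asymptomatic and would not have entered it.

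**The case against.** The strongest reply is that the protocol largely settles the matter.

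1. **The table is split by symptom status.** The bracket is a grade definition, and the block heading says which events the block is for. Canakinumab Table 6-28 carries the same bracket under the same kind of heading, which suggests carried-over grade text and not a decision to rechallenge symptomatic patients. The Amendment 3 summary, which records alignment of amylase and lipase grades to CTCAE v5.0, points the same way.
2. **One course satisfies Section 6.3.1.** A site that stops capmatinib and does not restart breaches neither the ban on deviating from interruptions and reductions nor the rule that discontinuation is mandatory where indicated. A site that restarts breaches the second. Arm 2 may stop one drug and keep the other, so discontinuation is workable.
3. **The practical reach may be nil.** Arm 2 was declared futile and closed (Section 4.1.1). The number still on capmatinib is not given.
4. **The subject counts measure a wider event.** They come from another study with CTCAE v4.03 grading. Arm 2 excludes lipase above ULN and amylase above grade 2, and whether the source study did the same is not stated.

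Point 2 stands: discontinuation is the defensible course. Points 3 and 4 stand as limits on size. Point 1 explains the likely origin but does not remove the conflict, because the grade 3 row names symptoms outright and the grade 4 row under the same heading is symptomatic. Closure does not lift the dosing rules from anyone still treated: Amendment 4 recorded arm 2 as closed and still added a capmatinib discontinuation rule to Table 6-23.

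**Conclusion.** The concern holds as a minor safety-wording correction. One cell of Table 6-16 gives a symptomatic rise of >2.0–5.0 × ULN an instruction to restart that the table's last row forbids, and no rule ranks the two.

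The conflict is binary (rechallenge or not), limited to rises that resolve to grade 2 or lower within 21 days, and limited to arm 2 subjects still on capmatinib, at most 43. The ceiling of about 1.8 subjects assumes that the single-agent lipase rate transfers to arm 2 and that v4.03 grades roughly match the v5 cell; the true number would be smaller. That discontinuation was intended is an inference from Section 6.3.1. Endpoints, analyses, sample size and the other arms are untouched.

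**What to change.** In the grade 3 row of Table 6-16, delete the part of the definition covering >2.0–5.0 × ULN with signs or symptoms, leaving only >5.0 × ULN and asymptomatic. Every symptomatic elevation then falls under the existing any-grade discontinuation row.

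The grade 4 row already orders the same action and may stay. Moving it into the symptomatic block would be tidier, because it would make the headings true. Table 6-28 needs no change: it has no any-grade symptomatic row, so this conflict does not arise there.

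The cost is one phrase in one cell, with no effect on visits, sample size or analyses.
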